11.2.2 Visualization of focal liver lesions

Visualization of focal liver lesions will be measured by the two variables 'lesion border delineation' (BD) and 'lesion contrast compared to liver background' (LC). Both variables will be determined by qualitative assessment on the following 4-point scales for up to 15 lesions per patient as defined in Section 6.2.3.1 of the protocol: 1='poor', 2='partial / moderate', 3='good', 4='excellent'.

For each reader, the two sum scores (sBD and sLC) are determined for each patient by summarizing the individual scores over all lesions detected by treatment groups UnMRI (unenhanced MRI), MeMRI (mangoral-enhanced MRI) and CMRI (combined mangoral-enhanced MRI plus unenhanced MRI). Both scores are weighted by the number of lesions per patient. Mean difference (sum score weighted by number of matched lesions) will also be derived for matched lesions: Unenhanced MRI vs. Combined MRI and Unenhanced MRI vs. Enhanced MRI.

The handling of MRI scans with more than 15 lesions is described in specific documents (MRI manual for training the investigators on MRI reading procedures and rules and Independent Review Charter) prepared for the independent reading process. If there are more than 15 lesions, the reader will start counting starting from the smallest lesion to the largest lesion and will stop at 15 lesions.

11.2.3 Confidence in lesion detection

Confidence in lesion detection will be evaluated for each lesion during the central reading sessions, i.e. part I (unenhanced MRI alone), part II (CMRI) and part III (mangoral-enhanced MRI alone), by 3 independent readers and by on-site radiologists. Up to 15 lesions per patient will be evaluated on 3-point scale:

- 1 = The lesion is detected with low confidence
- 2 = The lesion is detected with moderate confidence
- 3 = The lesion is detected with high confidence.

11.2.4 Confidence in lesion localization

Confidence in lesion localization will be assessed for each lesion during the central reading sessions (part I, part II and part III) by 3 independent readers and by on-site radiologists. Up to 15 lesions per patient will be evaluated on 3-point scale:

- 1 = The lesion is localized to a liver segment with low confidence
- 2 = The lesion is localized to a liver segment with moderate confidence

3 = The lesion is localized to a liver segment with high confidence.

Note: If a lesion is large enough to be present in more than 1 segment it shall be considered to be in the segment in which its center lies.

11.2.5 Quantitative assessments

For the quantitative analysis, the signal intensities (SI) of liver parenchyma and liver lesion as well as the standard deviation (SD) of the background noise will be determined by each of the three independent readers during central reading session part II (paired reading of both unenhanced and mangoral-enhanced images). The assessment will be done only during reading session part II as this allows the off-site readers to assess the same lesions on unenhanced and enhanced images. Up to 5 lesions per patient of ≥ 2 cm in diameter will be evaluated and these lesions will be the same on pre- and post-contrast images. If in a patient, all lesions are < 2 cm in diameter, only normal liver SI and background noise will be measured.

Quantitative SI will be measured by positioning circular regions of interest (ROIs) in a homogenous area in the liver and in the assessed liver lesion on the same image. The ROI placed in the lesion should at least encompass half of the lesion. ROIs of a constant size will be placed in the same locations on all pre- and post-contrast images. SD of the background noise will be measured using the largest possible rectangular ROI vertical to the patient's abdomen in the direction of the phase-encoding gradient.

The following quantitative measures will be determined:

Signal intensity (SI) enhancement:

- Liver SI enhancement (%) = $([SI_{liver} \text{ post contrast} - SI_{liver} \text{ pre contrast}]/[SI_{liver} \text{ pre contrast}]) \times 100$

Liver-to-lesion contrast (LLC):

- LLC = $(SI_{liver} - \text{Mean of } SI_{les})/(SI_{liver} + \text{Mean of } SI_{les})$

Signal-to-noise ratio (SNR):

- SNR = SI_{liver}/SD_{noise}

Contrast-to-noise ratio (CNR):

- CNR = $(SI_{liver} - \text{Mean of } SI_{les})/SD_{noise}$

with SI_{liver} = signal intensity of the liver, SI_{les} = signal intensity of the lesion, SD_{noise} = standard deviation of the background noise, Mean of SI_{les} is the mean of all lesion signal intensities for a patient.

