### 1.1.4 Mangoral

Mangoral is a manganese-based contrast agent for liver MRI developed for oral administration. It contains manganese (II) chloride tetrahydrate ( $MnCl_2 \cdot 4H_2O$ ) as its active pharmaceutical ingredient. As manganese is poorly absorbed from the intestine, L-alanine and vitamin D3 are included in the formulation and function as absorption promoters to increase the uptake of manganese into hepatocytes in the liver [13]. As manganese accumulates in the normal hepatocytes but not in liver metastases, the hypointense lesions are clearly visible against the hyperintense liver parenchyma on MRI images.

The advantage of the oral route of administration of manganese is its portal venous transport to the liver and its fast uptake into hepatocytes resulting in a very low systemic availability of manganese. As mainly the enterohepatic circulation is involved, the risk for toxicities in the central nervous system, heart, or kidney is drastically reduced.

To date, mangoral has been studied in 6 completed clinical Phase I and II trials in healthy volunteers ( $N = 52$ , in which 2 received placebo) and patients with known liver metastases or suspected liver lesions ( $N = 75$ ). An overview of these studies is given in [Table 1](#). In addition, 77 patients received mangoral in a compassionate use program based on referral diagnoses that involved different types of focal liver lesions and diseases of the intestines (e.g. different types of primary cancers with liver metastases, hepatocellular carcinoma, hemangiomas,

jaundice, cholangitis, infections, cysts and other diseases) regardless of kidney function. All patients in the compassionate use program received 1600 mg mangoral.

Taken together, the diagnostic efficacy analyses of the conducted clinical studies showed improved diagnostic quality scores after administration of mangoral. Compared to unenhanced liver MRI, administration of mangoral resulted in increased relative signal intensity in the liver, and improved delineation and visualisation of liver lesions. Dose-dependency was observed for some of the efficacy variables assessed, with the 800 mg dose giving the best balance between safety and efficacy. In comparison to an intravenous gadobenate dimeglumine protocol, mangoral was comparable in the sensitivity to detect colorectal cancer liver metastases.

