### 6.2.3.5 Quantitative assessments

For the quantitative analysis, the signal intensities (SI) of liver parenchyma and liver lesion, as well as the standard deviation (SD) of the background noise will be determined by each of the three independent readers during central reading session part II (paired reading of both unenhanced and mangoral-enhanced images; Section 6.2.5). The assessment will be done only during reading session part II as this allows the readers to assess the same lesions on unenhanced and enhanced images in the absence of formal lesion matching. Up to 5 lesions per patient of  $\geq 2$  cm in diameter will be evaluated and these lesions will be the same on pre-and post-contrast images.

Quantitative SI will be measured by positioning circular regions of interest (ROIs) in a homogenous area in the liver and the assessed liver lesion on the same image. The ROI placed in the lesion should at least encompass half of the lesion. ROIs of a constant size will be placed in the same locations on all pre- and post-contrast images. SD of the background noise will be measured using the largest possible rectangular ROI vertical to the patient's abdomen in the direction of the phase-encoding gradient.

The following quantitative measures will be determined:

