#### Liver-to-lesion contrast (LLC):

- $LLC = (SI_{liv} - SI_{les})/(SI_{liv} + SI_{les})$

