7.1 Changes from Protocol

The planned analysis will be performed according to the study protocol, its amendments and this statistical analysis plan. If there are contradictions between the study protocol or its amendments and this statistical analysis plan, the analysis will be performed according to this analysis plan. Any deviation from the planned analysis according to the study protocol has to be described in the integrated report.

The protocol states that the per protocol set is all patients in the full analysis set without any important protocol deviations. The SAP has been revised to state that only a subset of important deviations will result in patients being excluded from the per protocol set. All important protocol deviations will be manually reviewed by ICON and Ascelia to agree which could have impact on the per protocol set.

The protocol mentions the requirement for adverse drug reactions (defined per protocol as a causal relationship between a medicinal product and an AE to be at least a reasonable possibility) to be collected

and summarized. However, in this study adverse events are only assessed as related or not related so this will be used for the outputs.

The wording and definition of the PK dialysis subgroup population is amended.

The protocol Section 8.1.5 mentions subgroup analysis to be performed on the co-primary variables to be done by status of liver disease, on the subgroup of patients with PK data and also subgroup of patients with brain MRI, this is not included in the SAP as the patient groups are considered to be too small for a meaningful comparison. Subgroup analysis on the co-primary variables by sex will be added. Additionally subgroup analyses is mentioned in the protocol for by lesion diameter on the primary endpoint, this is not planned but different subgroup analyses is planned as described in [Section 13.6.3](#).

The derivations for liver-to-lesion contrast and contrast to noise ratio are amended slightly as described in [Section 11.2.5](#).

QTcB interval (msec) and QTcF interval (msec) were derived in the database but issues were found with these calculations, for this reason these parameters were re-derived in the datasets per the derivations in [Section 11.2.1](#).

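### SAP 11.2.5 gives each patient one signed LLC and one signed CNR from the mean lesion intensity, so lesions on opposite sides of liver signal cancel and a bright lesion that fades into the liver is tabulated as an increase

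*SAP*

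**What the plan says.** Protocol section 6.2.3.5 has each central reader place regions of interest "in a homogenous area in the liver and the assessed liver lesion on the same image". It defines LLC as liver minus lesion signal, divided by their sum, and CNR as liver minus lesion signal, divided by the noise SD. Both are signed and written with a single lesion intensity. The protocol does not say how several lesions in one patient are to be combined.

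SAP section 11.2.5 keeps the signed form and the selection rule, "Up to 5 lesions per patient of ≥ 2 cm in diameter will be evaluated", but replaces the lesion intensity with a quantity that "is the mean of all lesion signal intensities for a patient". The result is one LLC and one CNR per patient, reader and time point. It plans no absolute value, per-lesion summary or split by lesion polarity. SAP section 7.1 declares the change without a reason: "The derivations for liver-to-lesion contrast and contrast to noise ratio are amended slightly".

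The expected appearance, a dark lesion on a bright liver, is given in protocol section 1.1.4 for metastases: "As manganese accumulates in the normal hepatocytes but not in liver metastases, the hypointense lesions are clearly visible". The population is mixed by design. Protocol section 4 aims for about 20% HCC, and SAP section 13.7.3 distinguishes benign, HCC, metastatic and unknown lesions. T1, T2 and diffusion-weighted sequences are all acquired (protocol section 3), and neither quantitative section says on which one the regions are measured.

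**The concern.** A larger signed LLC or CNR means more visible only for lesions darker than liver. For a lesion brighter than liver the scale runs the other way: as the liver brightens towards it, the value climbs from negative to zero while the lesion disappears. Averaging over a patient with both kinds of lesion lets one offset the other, and a single value per patient does not show which lesion gained and which lost.

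Among the four quantitative measures, SI enhancement and SNR use liver signal only. LLC and CNR are the only ones that measure lesion against liver, so they are the natural measured companion to the reader-scored co-primary lesion contrast. If they can stay flat while every lesion becomes clearer, or rise while one vanishes, they are a weak companion in the patients concerned. The lesion-type subgroups in SAP section 13.7.3 cover the visualisation endpoints and not LLC or CNR, so no planned summary table would expose this.

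**Working it through.** The documents give no numerical value for LLC or CNR, and no sample size rests on them, so there is no stated figure to reproduce. The formulas are from SAP section 11.2.5. All intensities and the noise SD of 10 are assumed, for illustration.

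With L the liver signal, S_j the signal of lesion j, M the patient's mean lesion signal and σ the noise SD:

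- SAP: LLC = (L − M)/(L + M); CNR = (L − M)/σ.
- Per lesion, absolute: the average over j of |L − S_j|/(L + S_j), and of |L − S_j|/σ.

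**What pooling does by itself.** With one L and one σ, the average of (L − S_j)/σ equals (L − M)/σ. For CNR, pooling intensities first is therefore the same as averaging signed per-lesion CNRs; over 20,000 random draws the largest difference was 7e-15, which is rounding. For LLC the two differ, by at most 0.124 in those draws. The sign is thus the main source of distortion. Averaging adds the loss of lesion-level detail.

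**Cases (before → after contrast).**

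| Case | Liver | Lesions | SAP LLC | Mean absolute LLC | SAP CNR | Mean absolute CNR |
|---|---|---|---|---|---|---|
| 1. Dark and bright, both clearer | 100 → 150 | 70, 130 → 70, 230 | 0 → 0 | 0.153 → 0.287 | 0 → 0 | 3.0 → 8.0 |
| 2. Four dark, one bright | 100 → 150 | 75×4, 140 → 75×4, 260 | 0.064 → 0.145 | 0.148 → 0.320 | 1.2 → 3.8 | 2.8 → 8.2 |
| 3. One bright lesion fades | 100 → 130 | 130 → 130 | −0.130 → 0 | 0.130 → 0 | −3.0 → 0 | 3.0 → 0 |
| 4. Bright fades, dark clearer | 100 → 140 | 140, 60 → 140, 60 | 0 → 0.167 | 0.208 → 0.200 | 0 → 4.0 | 4.0 → 4.0 |
| 5. Two dark, one fades | 100 → 140 | 80, 80 → 80, 140 | 0.111 → 0.120 | 0.111 → 0.136 | 2.0 → 3.0 | 2.0 → 3.0 |
| 6. All dark, stay dark | 100 → 140 | 60, 80 → 60, 80 | 0.176 → 0.333 | 0.181 → 0.336 | 3.0 → 7.0 | 3.0 → 7.0 |

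Case 1 in full. Before: M = (70 + 130)/2 = 100 = L, so LLC = 0. Per lesion, 30/170 = 0.176 and −30/230 = −0.130, mean absolute value 0.153. After: M = (70 + 230)/2 = 150 = L, so LLC = 0 again. Per lesion, 80/220 = 0.364 and −80/380 = −0.211, mean absolute value 0.287.

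Case 2. M goes from 88 to 112, so LLC is 12/188 = 0.064 and then 38/262 = 0.145. The gain is 0.081, against 0.172 on the absolute per-lesion scale, which is less than half.

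Case 3. LLC goes from −30/230 = −0.130 to 0/260 = 0. There is only one lesion, so averaging plays no part.

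**Range for a fading bright lesion.** For a lesion fixed at 140 and a liver starting at 100, liver enhancement of 10%, 20%, 40% and 60% changes the signed LLC by +0.047, +0.090, +0.167 and +0.233. Absolute LLC changes by −0.047, −0.090, −0.167 and −0.100.

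A single dark lesion that fades (80 → 140, liver 100 → 140) is correctly shown as a fall: LLC 0.111 → 0 and CNR 2 → 0.

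**The case against.** Much of the case on the other side stands.

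- **The false gain for a single bright lesion is not the SAP's doing.** It follows from the signed formula in the protocol. A reader might infer that the averaging step creates it. Case 3 and the CNR identity show otherwise.
- **Absolute values alone are not a cure.** In case 5 the mean of absolute values rises just as the SAP value does, and for LLC by more (0.111 to 0.136, against 0.111 to 0.120). In case 4 mean absolute CNR stays at 4.0 while one lesion vanishes. Any patient mean can hide one lost lesion.
- **The intensities are assumed.** Cases 1 and 2 need a bright lesion to enhance more than the liver (130 → 230 is +77% and 140 → 260 is +86%, against +50%). Nothing in the documents supports that size of uptake. Cases 3 and 4 need only a lesion that starts brighter than liver, and how often that happens is not stated either.
- **Silence on the sequence proves little.** Protocol sections 3 and 6.2.4.2 leave the reading method to the imaging manual and the review charter, which may name it. Nor do the documents say how many liver regions are recorded per patient, so they do not show that the same-image pairing of liver and lesion is lost.
- **The results are descriptive.** No rule defines improvement in LLC or CNR, SAP section 7.1 declares the amendment, and SAP section 10.1 promises full listings.

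What remains is that the stated derivation gives a misleading value when lesions lie on both sides of liver signal, or when one that starts brighter than liver fades. The trial deliberately mixes lesion types. The sponsor itself expects them to respond differently: SAP section 9.3 assumes half the effect in HCC, in up to 30% of patients. Listings let a reader find such a patient, but the summary table will not show it.

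**Conclusion.** The point holds as a defect in two secondary descriptive measures. Where lesions lie on both sides of liver signal, the patient-level LLC and CNR understate contrast, down to nil in the extreme. Where a lesion starts brighter than liver and fades, the signed change has the wrong direction: +0.130 in LLC in case 3, and +0.047 to +0.233 over liver enhancement of 10% to 60%. These sizes rest on assumed intensities. Where all lesions are dark and stay dark, the SAP values differ from per-lesion values by about 0.004 in LLC and not at all in CNR (case 6).

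Two stronger conclusions might be drawn, and the documents support neither. One is that LLC and CNR cannot support or contradict the primary result. Only an unknown share of patients is distorted, so that does not follow. The other is that the efficacy conclusion is at risk. The co-primary tests use reader scores and are unaffected, as are the significance level and the sample size.

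**What to change.** In SAP section 11.2.5:

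1. Derive LLC and CNR for each lesion, using the liver region from the same image if several are recorded and otherwise the patient's single liver value. Report the patient mean of the absolute values.
2. Alongside it, report signed per-lesion values by baseline polarity (darker or brighter than liver), and the number of lesions whose absolute contrast rose or fell. These show a fading lesion, or one that flips from dark to bright, which a mean of absolute values can hide.
3. Keep the pooled signed version as supportive.
4. State the sequence on which the regions are measured, even if the review charter already does.

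The cost is SAP wording, programming and a few more tables, since lesion intensities are already measured. One limitation should be stated: absolute values carry a positive noise floor that is larger when contrast is near zero, so they can slightly understate a gain from a near-nil baseline.

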11.3 Statistical Software

All statistical analyses will be performed with SAS®, Version 9.4 or later. Working instructions are printed in the highlighted italic text below the shells.

12.0 Interim Analyses

No interim analysis is planned.

13.0 Statistical Methods

13.1 Patient Disposition

Patient disposition will be tabulated with number and percentages of patients enrolled, dosed, completed according to the protocol (completion of Visit 7 if part of the brain MRI subgroup population, otherwise completion of Visit 6) or discontinued prematurely. The patients who prematurely discontinued the study and the reasons for their discontinuation will be presented. The number and percentage of patients screened, not enrolled and reasons for non-enrollment will also be presented. The number and percentage of patients in each analysis population will also be presented as part of the disposition output.

13.2 Protocol Deviations

Protocol deviations will be summarized based on the assessment of major (important) or minor (non-important) by type for the SAF, FAS and PPS populations. In addition, for the subset of patients with major (important) or minor (non-important) deviations we will present the number and percentage who completed the study and those who discontinued the study.

All protocol deviations will be listed.

13.3 Demographic Data and Baseline Characteristics

The demographic data and baseline characteristics will be analyzed using descriptive statistics in summary or frequency tables for the following parameters for the SAF, FAS and PPS populations:

- Sex
- Age
- Age group (≥ 18 - < 65 years, ≥ 65 - < 75 years and ≥ 75 years)
- Ethnicity
- Race
- Height (cm)
- Weight (kg)
- BMI (kg/m^2)

The screening laboratory results will also be summarized for the SAF, FAS and PPS populations showing the below:

- Laboratory results related to GFR (eGFR categorization, eGFR value). Serum creatinine, serum albumin and serum urea nitrogen values are recorded in the source documents at site for assessing GFR but will not be summarized.
- Laboratory results related to Child-Pugh scoring (Child-Pugh score, encephalopathy grade, ascites, serum bilirubin, serum albumin and INR) by liver disease based on medical history records.

Disease history of focal liver lesions will be summarized and also listed.

13.4 Medical History and Signs and Symptoms

All general medical history conditions, surgical history and signs and symptoms will be coded in MedDRA version 25.0 or higher. General medical history conditions and signs and symptoms will be summarized by system organ class and preferred term for the SAF, FAS and PPS populations. The version of the utilized dictionary will be presented as part of the provided tables and listings.

All medical history, surgical history and signs and symptoms will be listed. Any medical history marked as ongoing on the CRF or with a missing end date will be considered as "ongoing".

13.5 Prior and Concomitant Medications

Prior and concomitant medications will be coded according to the World Health Organization (WHO) Drug Dictionary (2022MAR GLOBAL B3) or later and summarized frequencies and percentages according to ATC level 2 and preferred term for the SAF, FAS and PPS populations. Patients taking the same medication multiple times will be counted once per medication. The version of the utilized dictionary will be presented as part of the provided tables and listings.

13.6 Investigational Medicinal Product Compliance and Accountability

IMP administration will be summarized for the SAF, FAS, PPS and PKS. Frequencies and percentages and/or descriptive statistics will be provided for each category. In addition, the number and percentage of patients receiving 200 mL of IMP as planned per protocol will be provided.

13.7 Efficacy Analysis

13.7.1 Primary Efficacy Analysis

The primary population for this analysis will be the full analysis set (FAS). The two sum scores (sBD and sLC) are determined for each patient (both combined and unenhanced) by summarizing the individual scores over matched lesions. Then, the mean score differences between the paired sum scores weighted by the number of matched lesions are determined per patient:

$$\text{Diff(BD)} = \frac{s\text{BD}_{\text{combined}} - s\text{BD}_{\text{unenhanced}}}{\text{Number of lesions}}$$

$$\text{Diff(LC)} = \frac{s\text{LC}_{\text{combined}} - s\text{LC}_{\text{unenhanced}}}{\text{Number of lesions}}$$

For each independent reader, the hypotheses for the superiority of CMRI versus unenhanced MRI will be tested using a 1-sided paired t-test using the means of paired score differences:

$$H_{0;\text{BD}}: \mu \text{Diff(BD)} \leq 0 \quad \text{versus} \quad H_{1;\text{BD}}: \mu \text{Diff(BD)} > 0$$

and

$$H_{0;\text{LC}}: \mu \text{Diff(LC)} \leq 0 \quad \text{versus} \quad H_{1;\text{LC}}: \mu \text{Diff(LC)} > 0$$

If both tests indicate superiority of CMRI at the 1-sided significance level of 0.025, reader success is achieved. The corresponding 2-sided 95% confidence intervals will be also calculated. These results will be presented in a table together with a summary of the mean scores per reader.

Additionally, as a sensitivity analysis, the analogous 1-sided Wilcoxon signed rank test will be performed. The primary analysis will be also repeated in an exploratory manner for the per protocol set using the above-described methodology.

Superiority of CMRI over unenhanced MRI regarding visualization of focal liver lesions will be analyzed by testing the superiority of each of the two co-primary variables separately for each of the three independent readers. Reader success will be achieved if the reading results of a reader demonstrate superiority of CMRI versus unenhanced MRI for both lesion border delineation and lesion contrast. The acceptance by two out of three readers will be considered to be a successful demonstration of efficacy in the study.

